9.3 Secondary Objectives

To assess correlation between OBT with or without MBT with or without other available biomarkers and disease course, defined by clinical outcomes, at 18 and 36 months.

Exalenz Bioscience Ltd.	Last update on: May1, 2016
Study Title: Clinical Study of the BreathID [®] System to train the algorithm for the ¹³ C-Octanoate Breath Test with or without the ¹³ C-Methacetin Breath Test (OBT and MBT respectively) for correlation with histological findings of Non-Alcoholic Fatty Liver Disease (NAFLD)	Protocol No.: NASH-EX-1114
	Version: 1f
Document N^o: CSD00080	Page 26 of 61

9.4 Efficacy Endpoints

9.4.1 Primary efficacy endpoint

Correlation of histological findings, as assessed by a central reader, of NAFLD compared to ¹³C-Octanoate Breath Test with or without ¹³C-Methactin Breath Test with or without additional clinical and/or laboratory parameters.

9.4.2 Secondary efficacy endpoint

Correlation between OBT with or without MBT and clinical course (i.e. clinical outcome: liver decompensation events etc.) at 18 and 36 months post the last breath test performed (visit / phone).

NOTE: Patients undergoing intervention for NASH / NAFLD, including both approved and experimental approaches prior to the defined time points will be terminated hence will not be evaluated for this endpoint.

9.5 Safety Endpoints

Safety will be assessed by assessing all adverse and serious adverse events occurring in all subjects enrolled from the time of enrollment until the subject completes the protocol.

Any AEs reported that are possibly or probably related to the use of the product or related to the procedure within 36 months post last breath test performed or until subject termination will be followed until resolution and if laboratory work is done secondary to AEs and found abnormal, these tests will be followed until normalization or stabilization.

10 SUBJECT SELECTION

The study population will be enrolled on a consecutive basis of able and willing subjects with a fresh up-to-standard liver biopsy (i.e. tissue sample biopsied within 6 months prior to the OBT and MBT and evaluated for quality prior to enrollment), indicated to rule-out / confirm NAFLD, meeting all inclusion/exclusion criteria.

Patients to be enrolled in the proposed study will be from centers in Europe and the US. It is presumed patients on both continents have similar disease phenotypes and prognosis and the produced data can be used interchangeably in this multicenter clinical trial investigating NAFLD populations.

Exalenz Bioscience Ltd.	Last update on: May1, 2016
Study Title: Clinical Study of the BreathID [®] System to train the algorithm for the ¹³ C-Octanoate Breath Test with or without the ¹³ C-Methacetin Breath Test (OBT and MBT respectively) for correlation with histological findings of Non-Alcoholic Fatty Liver Disease (NAFLD)	Protocol No.: NASH-EX-1114
	Version: 1f
Document N^o: CSD00080	Page 27 of 61

10.1 Inclusion Criteria

1. Adult men or women (≥ 18 years of age)
2. Liver biopsy indicating NAFLD/NASH performed within 6 months prior to both breath-tests
NOTE: The samples must meet pre-defined quality criteria. (See Appendix II for biopsy quality requirements)
OR:
Undergoing Liver biopsy to rule-out or confirm NAFLD/NASH.
3. No other known co-existent liver disease, excluded by appropriate serologic / other testing
4. Patient able and willing to sign an Informed Consent Form
5. Can tolerate an overnight (8-hour) fast

10.2 Exclusion Criteria:

1. Positive studies for any of the following within three years prior to biopsy
 - a. Anti HCV positive
 - b. HBsAg positive
 - c. Iron saturation $> 60\%$ + gene test for hereditary hemochromatosis or iron overload as defined by presence of 3+ or 4+ stainable iron on liver biopsy
 - d. Antinuclear antibody at a titer $> 1: 160$ along with hypergammaglobulinemia and 5 times ALT normal levels
 - e. Alpha-1-antitrypsin level below lower limit of normal (< 150 mg/dl) or no PAS diastase resistant globules on biopsy.
 - f. Primary biliary cirrhosis as defined by elevation of alkaline phosphatase greater than upper limit of normal and anti-mitochondrial antibody (AMA) of greater than 1:80 and consistent liver histology
 - g. Low level of ceruloplasmin (< 10 ng/mL)
 - h. Drug-induced liver disease as defined on the basis of typical exposure and history
Note: these studies do not need to be performed if they are not available, as it is assumed that if they are not on file, the condition does not exist.
2. Patients known to have chronic liver disease other than NAFLD as routinely diagnosed by the investigator
3. Concurrent acute hepatic condition other than NAFLD

Exalenz Bioscience Ltd.	Last update on: May1, 2016
Study Title: Clinical Study of the BreathID [®] System to train the algorithm for the ¹³ C-Octanoate Breath Test with or without the ¹³ C-Methacetin Breath Test (OBT and MBT respectively) for correlation with histological findings of Non-Alcoholic Fatty Liver Disease (NAFLD)	Protocol No.: NASH-EX-1114
	Version: 1f
Document N^o: CSD00080	Page 28 of 61

4. Alcohol consumption > 20 gm/day (0.71 oz./day) for women and > 30 gm/day (1.06 oz./day) for men
5. Drugs that may interfere with octanoate metabolism or that can also cause NAFLD independent of the metabolic syndrome, including: corticosteroids, amiodarone, tetracycline, valproic acid, methotrexate, stavudine, zidovudine
6. When MBT is performed, subject should not have taken any of the following at least 48 hours prior to the breath test: Acyclovir , allopurinol, carbamazepine, cimetidine, ciprofloxacin, daidzein, (herbal) disulfiram, echinacea, enoxacin, famotidine, fluvoxamine, methoxsalen, mexiletine, montelukast, norfloxacin, phenylpropanolamine, phenytoin, propafenone, rifampin, terbinafine, ticlopidine, thiabendazole, verapamil, zileuton or any medication that might interfere with Methacetin metabolism or might affect CYP 1A2
7. Patients that have had more than 10% weight change between biopsy and enrollment.
8. Hypersensitivity to any of the study substrates: Octanoate or Methacetin and their metabolites, i.e. paracetamol, acetaminophen
9. Known extra-hepatic diseases including but not limited to: severe congestive heart failure (NIHA>2), known severe pulmonary hypertension (>35 mmHg), history of chronic obstructive pulmonary disease or uncontrolled symptomatic bronchial asthma or uncontrolled diabetes mellitus (HA1c>9.5%)
10. Previous surgical GI bypass surgery
11. Extensive small bowel resection (>100 cm)
12. Known uncontrolled malabsorption or diarrhea
13. Concurrent total parenteral nutrition
14. Any organ transplant
15. Patients receiving any anti-viral treatment or any other liver directed therapy, procedure or surgery between the time of the biopsy and the breath test
16. Pregnant or breast feeding
17. Patients unable or refusing to sign informed consent
18. Patients that, based on the opinion of the investigator, should not be enrolled into this study due to safety / adherence reasons
19. Patients participating in other clinical trials and already receiving experimental treatments or procedures

Exalenz Bioscience Ltd.	Last update on: May1, 2016
Study Title: Clinical Study of the BreathID [®] System to train the algorithm for the ¹³ C-Octanoate Breath Test with or without the ¹³ C-Methacetin Breath Test (OBT and MBT respectively) for correlation with histological findings of Non-Alcoholic Fatty Liver Disease (NAFLD)	Protocol No.: NASH-EX-1114
	Version: 1f
Document N^o: CSD00080	Page 29 of 61

20. Patients with suspected or documented hepatocellular carcinoma by ultrasound or other imaging modality
21. Patients diagnosed with partial / complete portal venous occlusion, hepatic venous occlusion, previous PHT surgery, or placement of a trans-jugular intrahepatic porto-systemic shunt (TIPS) according to initial imaging studies

10.3 On the day of the OBT:

1. Eight (8) hours fasting prior to OBT including all PO morning medications except for beta blockers. Diabetic patients that are driving should test their blood sugars to rule out hypoglycemia and respond accordingly.
2. No general anesthesia or sedation within 24 hours prior to OBT
3. No alcohol within 24 hours prior to OBT
4. Patient should be symptom free of any prior intervention (e.g. biopsy)

10.4 On the day of the MBT:

1. Eight (8) hours fasting prior to MBT including all PO morning medications except for beta blockers. Diabetic patients that are driving should test their blood sugars to rule out hypoglycemia and respond accordingly.
2. No smoking on the day of the MBT
3. No paracetamol (acetaminophen) based medications within 24 hours prior to MBT
4. No general anesthesia or sedation within 24 hours prior to MBT
5. No alcohol within 24 hours prior to MBT
6. Patient should be symptom free of any prior intervention (e.g. biopsy)

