12 STUDY PROCEDURES

12.1 General

1. The study will be conducted in compliance with this protocol, in concordance with GCP standards, and applicable regulatory requirements.
2. The study design is: cross-sectional, enrolling patients in a consecutive manner per site, so as to prevent any bias.
3. Patients will sign a consent/assent form prior to study participation
4. An eCRF will be completed for each subject.
5. The raw data will be saved on the *BreathID*[®] device.
6. All patients undergoing liver biopsy to rule-out or confirm NAFLD, within 6 months prior to breath tests and within 1 month after first breath test, should be considered for enrollment. If the biopsy is done on the day of one of the breath tests, the breath test must precede the biopsy.
7. Biopsy slides of enrolled patients may undergo high-resolution scanning to simplify central reading and filing.
8. All tissue slides or their respective scans if relevant, will be read twice; once by the local (study site) pathologist and once by the central reading laboratory. In case of discrepancy the central reading results prevail. The characteristics to record for each sample are specified within Appendix II to this protocol. All parameters will be entered into the study eCRF.
9. Any adverse events will be recorded according to GCP ICH guidelines. Section 0 below¹⁵ below relates to the reportable and non-reportable SAEs.
10. All investigators will be blinded to the OBT and MBT results until the end of the study recruitment. This is to ensure that OBT and MBT results will not affect the current patient management. Hard copies of the device printouts will be stored separately from the other source data and the section within the eCRF containing the

Exalenz Bioscience Ltd.	Last update on: May1, 2016
Study Title: Clinical Study of the BreathID [®] System to train the algorithm for the ¹³ C-Octanoate Breath Test with or without the ¹³ C-Methacetin Breath Test (OBT and MBT respectively) for correlation with histological findings of Non-Alcoholic Fatty Liver Disease (NAFLD)	Protocol No.: NASH-EX-1114
	Version: 1f
Document N^o: CSD00080	Page 36 of 61

breath tests results will remain inaccessible to the treating physician (i.e. the investigator login will keep this section hidden).

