12.2 Visit 1: Screening / enrollment

1. Pre-screening for inclusion / exclusion criteria
2. As part of eligibility, biopsy slides should be "up to standard" according to the quality requirements specified within Appendix II to this protocol. (Biopsy quality requirements are as follows: Unfragmented needle core \geq 20mm length with \geq 10 portal tracts is recommended, according to the AASLD practice guidelines or equivalent.)
3. A minimum of Hematoxyline & Eosine (H&E) and Masson's trichome stained slides should be available. Additional optional stains include: Chromotrope Aniline blue (connective tissue), Prussian blue (iron storage), Sirius red stain (for fibrosis) and SMA will be filed if available. Additional unstained slides are recommended.
4. Histology slides or their respective scans, will be assessed by both the local pathologist and a central reader according to the parameters listed within Appendix II to this protocol. In case of significant differences in the assessment the central reader will always prevail.
5. Consenting patient.
6. Complete study eligibility and enrollment.
7. Physical or high resolution scanned slides sent to local and central reading according to Appendix II.

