12.3 Visit 2: ¹³C-Octanoate Breath Test (OBT)

1. Female patients of childbearing age meeting all criteria will undergo pregnancy test if not available from the past 7 days. Abstinence or oral contraceptives are requested until completion of MBT (second breath test).

Exalenz Bioscience Ltd.	Last update on: May1, 2016
Study Title: Clinical Study of the BreathID [®] System to train the algorithm for the ¹³ C-Octanoate Breath Test with or without the ¹³ C-Methacetin Breath Test (OBT and MBT respectively) for correlation with histological findings of Non-Alcoholic Fatty Liver Disease (NAFLD)	Protocol No.: NASH-EX-1114
	Version: 1f
Document N^o: CSD00080	Page 37 of 61

2. OBT will be performed within 6 months post liver biopsy.
3. Medical History including the following:
 - a. Demographics
 - b. Detailed medical history including liver directed and other concomitant diseases (cardiovascular, respiratory, renal and neurological), presentation, interventions, etiology, habits etc.
 - c. Imaging results,- (if available) Ultrasound, CT and/or MRI, (liver outline, vasculature, evidence of fat etc.), imaging of major hepatic vessels, pancreas, intestines, and liver volume
 - d. Other assays: e.g. HVPG
 - e. Most recent laboratory blood test results within 6 months.
 - f. Concomitant medications
4. Physical examination (targeting liver related findings) including liver related clinical scoring.
5. In preparation for the OBT:
 - a. Eight (8) hours fasting prior to OBT including all PO morning medications except for beta blockers. Diabetic patients that are driving should test their blood sugars to rule out hypoglycemia and respond accordingly.
 - b. No general anesthesia or sedation within 24 hours prior to OBT
 - c. No alcohol within 24 hours prior to OBT
 - d. Patient should be symptom free of any prior intervention (e.g. biopsy)
6. Within one hour prior to the OBT blood will be drawn for the following panels (note the relevant remarks):
 - a. Insulin and Glucose
 - b. Complete Blood count (WBC, Hemoglobin, Platelets) and CRP
 - c. Coagulation: PT (INR)

Exalenz Bioscience Ltd.	Last update on: May1, 2016
Study Title: Clinical Study of the BreathID [®] System to train the algorithm for the ¹³ C-Octanoate Breath Test with or without the ¹³ C-Methacetin Breath Test (OBT and MBT respectively) for correlation with histological findings of Non-Alcoholic Fatty Liver Disease (NAFLD)	Protocol No.: NASH-EX-1114
	Version: 1f
Document N^o: CSD00080	Page 38 of 61

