12.4 Visit 3: ¹³C-Methacetin Breath Test (MBT)

1. MBT will be conducted within 6 months post liver biopsy and within 30 days of the OBT but not less than 48 hours post OBT.
2. In preparation for the MBT:
 - a. Eight (8) hours fasting prior to MBT including all PO morning medications except for beta blockers. Diabetic patients that are driving should test their blood sugars to rule out hypoglycemia and respond accordingly.
 - b. No smoking on the day of the MBT
 - c. No paracetamol (acetaminophen) based medications within 24 hours prior to MBT
 - d. No general anesthesia or sedation within 24 hours prior to MBT
 - e. No alcohol within 24 hours prior to MBT
 - f. Patient should be symptom free of any prior intervention (e.g. biopsy)

3. ¹³C-Methacetin Breath Test:

NOTE: Expected warm-up time for the device to be ready to measure patient's breath is up to 90 minutes. Ensure the device is turned on at least 2 hours prior to scheduled patient visit.

The breath test is performed automatically while the patient is connected to the device using a nasal cannula. The test is of 2 phases: baseline and the sampling phase separated by the administration of the test substrate. The 2 phases' durations are up to 30 and up to 60 minutes respectively.

Exalenz Bioscience Ltd.	Last update on: May1, 2016
Study Title: Clinical Study of the BreathID [®] System to train the algorithm for the ¹³ C-Octanoate Breath Test with or without the ¹³ C-Methacetin Breath Test (OBT and MBT respectively) for correlation with histological findings of Non-Alcoholic Fatty Liver Disease (NAFLD)	Protocol No.: NASH-EX-1114
	Version: 1f
Document N^o: CSD00080	Page 40 of 61

For more information regarding the OBT procedure please refer to Section 5 of the Investigator's Brochure.

4. Adverse events recording until the subject completes the protocol.
NOTE: Any AEs reported that are possibly or probably related to the use of the product or related to the procedure within 36 months post last breath test performed or until subject termination will be followed until resolution and if laboratory work is done secondary to AEs and found abnormal, these tests will be followed until normalization or stabilization.
5. Diabetic patients will be followed throughout the entire visit and should be instructed to resume their medication immediately after the breath tests.

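### Exclusion 7 stops counting weight change at enrollment, although the breath tests compared with the biopsy come later

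*Combined protocol and SAP*

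**What the plan says.** Section 10.2, item 7, and the same item in the synopsis exclude "Patients that have had more than 10% weight change between biopsy and enrollment". Item 15 of the same list, on antiviral treatment and "any other liver directed therapy, procedure or surgery between the time of the biopsy and the breath test", ends at the test instead.

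The visit text fixes the order of events:

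- Visit 1 (12.2): "Complete study eligibility and enrollment".
- Visit 2 (12.3): "OBT will be performed within 6 months post liver biopsy".
- Visit 3 (12.4): "MBT will be conducted within 6 months post liver biopsy and within 30 days of the OBT but not less than 48 hours post OBT".

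Section 12.1, item 6, also admits patients biopsied after testing has begun: a biopsy "within 6 months prior to breath tests and within 1 month after first breath test, should be considered for enrollment".

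The test-day conditions (10.3 and 10.4) cover fasting, sedation, alcohol and freedom from symptoms, and for MBT also smoking and paracetamol. They do not mention weight. Visit 2 includes a "Physical examination (targeting liver related findings) including liver related clinical scoring", with no comparison to weight at biopsy. The primary analysis set (11.6) requires a valid biopsy, valid OBT and MBT results and the biomarkers. It has no condition on weight change after enrollment.

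**The concern.** The primary endpoint compares each patient's breath values with one biopsy. That is sound only if the biopsy still describes the liver on the day of the test. Item 7 appears to serve that purpose: the plan has judged that a change of more than 10% makes the biopsy an unsafe reference, and section 5.1.1 links NAFLD to obesity and BMI. A change of that size matters as much the day after enrollment as the day before, yet the criterion ends at an administrative date.

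What is at stake is the quality of the pairs used to train the algorithm and choose its cut-off. Mismatched pairs weaken the observed association. Section 11.7.5 sets the minimum acceptable AUC at 0.75, the same value that section 11.5 assumes for the sample size.

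**Working it through.** **1. The intervals side by side**

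| Rule | Starts | Ends |
|---|---|---|
| Item 7, weight change over 10% | Biopsy | Enrollment (Visit 1) |
| Item 15, liver-directed therapy | Biopsy | Breath test |
| Inclusion 2, first branch | Biopsy, up to 6 months before | Both breath tests |

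**2. Time that item 7 leaves open**

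- MBT is at least 48 hours after OBT, and OBT is not before Visit 1. MBT is therefore always outside item 7's interval.
- If Visits 1 and 2 share a day, the open time is 48 hours to 30 days, up to MBT.
- If Visit 2 is later, OBT is outside as well. The readable text sets no limit from Visit 1 to Visit 2. For a patient enrolled soon after biopsy, only the six-month window bounds the gap.
- If the biopsy follows the first breath test, there is no interval from biopsy to enrollment at Visit 1, so item 7 cannot be applied.

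**3. The plan's precision figure, reproduced**

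Inputs from 11.5: AUC A = 0.75, at least 50 patients per class, 95% confidence. The Hanley-McNeil formula is

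SE² = [A(1−A) + (n₁−1)(Q₁−A²) + (n₀−1)(Q₂−A²)] / (n₁n₀), with Q₁ = A/(2−A) = 0.6 and Q₂ = 2A²/(1+A) = 0.6429.

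For 50 and 50: SE² = (0.1875 + 49×0.0375 + 49×0.08036)/2500 = 0.002385, so SE = 0.0488. The half-width is 1.96×0.0488 = 0.096, which agrees with the stated 0.1. At 50 and 150 it is 0.085.

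**4. Illustration of dilution (assumed shares; the documents give none)**

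Suppose a share p of NASH-labelled patients gives breath values exactly like those of non-NASH patients. Those patients discriminate at 0.5, so observed AUC = (1−p)×0.75 + p×0.5 = 0.75 − 0.25p.

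| p | Observed AUC | Loss | Loss / 0.1 half-width |
|---|---|---|---|
| 3% | 0.7425 | 0.0075 | 0.075 |
| 5% | 0.7375 | 0.0125 | 0.125 |
| 10% | 0.7250 | 0.0250 | 0.25 |

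Full conversion is the extreme case, so each row is an upper bound for that share of that class.

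A harsher model makes a share s of labels wrong at random in both classes. Observed AUC is then 0.5 + 0.25(a + b − 1), where a and b are the proportions of correct labels among observed positives and negatives. With equal classes this gives 0.740, 0.725 and 0.700 at s = 2%, 5% and 10%. With 50 against 150 it gives 0.734, 0.712 and 0.679.

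**5. What the fix would cost in precision**

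If both classes fell from 50 to 46, the same formula gives SE = 0.0509 and a half-width of 0.0998, still 0.1.

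**The case against.** Several objections have force.

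- **The visit schedule.** The overview in section 4 has no readable content in the copy reviewed. It may set a Visit 1 to Visit 2 window or list a weight measurement. With a short window, the open time would be little more than the OBT-to-MBT interval of at most 30 days. This stands and limits confidence in how long the gap is. It does not change where item 7 ends.
- **The long gap.** A reader might infer that a gap of nearly six months is usual. The text permits it, but nothing shows it is typical. For patients enrolled late in the window, item 7 already covers most of the time.
- **Direction of error.** A reader might infer that newly diagnosed NASH patients lose weight, so that the error concentrates in one class. No section says so, and item 7 counts gains as well as losses.
- **The 0.75 criterion.** A reader might infer that the gap pushes the AUC below the plan's minimum. That follows only if the true AUC is placed exactly at 0.75, where any noise would do the same; section 11.5 calls that value conservative.
- **Other safeguards.** Sections 11.5 and 11.7.6 plan periodic checks for factors affecting the correlation, and the algorithm will be validated in a separate study. These help in part, but a check on weight change needs a weight at the test, and the readable text does not name one.
- **Item 15.** It closes the route through liver-directed therapy. Whether prescribed diet counts as such therapy is undefined, so some patients with weight loss might already be excluded.
- **Late biopsies.** The biopsy must come within one month after the first breath test, which leaves little time for a change above 10%.

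**Conclusion.** The point holds as an inconsistency that is cheap to repair. Item 7 ends at enrollment, while item 15 and the biopsy window end at the tests. Nothing in the readable text closes the difference, at the test visits or in the primary set. For biopsies done after testing begins, the criterion cannot be applied at enrollment at all.

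The size is unknown. The documents give neither the actual enrollment-to-test interval, nor how often weight changes by more than 10% within it, nor what such a change does to breath values. If few patients are affected, the effect on the AUC is probably modest: under the one-class illustration the loss is at most 0.025 at an assumed 10%, a quarter of the planned half-width. Even the harsher two-class model stays inside 0.1 at that share (largest loss 0.75 − 0.679 = 0.071). The documents do not support a claim that the primary result would be overturned or that the cut-off would be biased in a known direction.

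**What to change.** 1. In section 10.2 and the synopsis, let item 7 measure the change of more than 10% from the biopsy to either breath test, in whichever order they occur. The threshold stays as the plan has it.
2. Record weight at Visits 2 and 3, and at the biopsy when it comes after a breath test.
3. In section 11.6, state that biopsy and breath-test pairs beyond the limit are left out of the primary set and kept in the secondary (ITT) set. Add a sensitivity analysis that includes them with the primary set.
4. Check that the visit schedule in section 4 agrees with the revised wording.

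The cost is a short amendment and a weight at two visits, plus one at any later biopsy. A few enrolled patients will leave the primary set, with a slight loss of precision. Because section 11.5 counts evaluable patients, the plan should say whether they are replaced. The sensitivity analysis shows whether leaving them out changes the result.
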